#### 5.4.2 Non-hematological toxicities

Toxicity	Adverse event	Dose Reduction/Delay	
		Eribulin	Lenvatinib
Hepatic toxicities	Grade 3/4 toxicity of AST/ALT/ Total bilirubin	If during treatment there is grade 3/4 liver toxicity then dose reduce by 1 dose level.	Hold until recovery to Grade 1 or baseline. Resume at reduced dose of 14 mg po daily if first occurrence, reduce to 10 mg po daily on second occurrence and 8 mg po daily on third occurrence.
Peripheral neuropathy	Grade 3 or 4	Hold until recover to ≤ grade 2. Reduce dose by one dose level. If neuropathy fails to recover to grade 2 within 3 weeks, eribulin should be discontinued.	No modifications necessary
Nonhematologic toxicity grade 3 or 4 attributed	Grade 3 or 4 nausea/ vomiting despite optimal	Hold until nausea/ vomiting have resolved to	Hold until nausea/ vomiting have resolved to ≤ grade 1. Resume at same

to any or all treatment (except for neuropathy)	antiemetic treatment	≤ grade 1. Resume at same dose level.	dose
	> Grade 2 stomatitis	Hold until stomatitis has resolved to ≤ Grade 1. Resume at one dose level below current dose level	Hold until recovery to ≤ grade 1. Resume at the same dose level
Hypertension	Grade 3 hypertension or life-threatening hypertension	No dose modification necessary	Withhold lenvatinib for Grade 3 hypertension that persists despite optimal antihypertensive therapy; resume at one dose level below current dose level. Discontinue for life-threatening hypertension
Cardiac dysfunction or hemorrhage	Grade 3 or 4 events	No dose modification necessary	Withhold lenvatinib for the development of Grade 3 event until improved to Grade 0 or 1 or baseline. Either resume at a reduced dose or discontinue lenvatinib depending on the severity and persistence of the adverse event
Proteinuria	Grade 3 or nephrotic syndrome (see footnote)	No dose modification necessary	Withhold lenvatinib until ≤ Grade 2 (proteinuria 2+ or 3+ or 24-hour urinary protein < 3.5g). Resume at next dose below current dose. Discontinue lenvatinib if nephrotic syndrome.
QTc prolongation	Grade 3 or greater	No dose modification necessary	Monitor and correct electrolyte abnormalities in all patients. Withhold lenvatinib for the development of Grade 3 or

			greater QT interval prolongation. Resume lenvatinib at one dose level below the current dose when QTc prolongation resolves to Grade 0 or 1.
Hand foot syndrome	Grade 2	No modification necessary	Withhold until $\leq$ Grade 1. Resume at the same dose or below current dose at physicians discretion
	Grade 3/4	No modification necessary	Withhold until $\leq$ Grade 1. May resume at the same dose or below current dose at physicians discretion

- For other grade 3/4 non-hematological toxicities not specifically mentioned in the table: the investigator could decrease the dose of the responsible drug after returning to grade 1 at the physician's discretion.
- If a patient has simultaneous multiple grade 2 adverse events or an intolerable grade 2 adverse events as per CTCAE, the investigator could decrease the dose of the responsible drug after discussion with the Principal Investigator and adjust according to 5.4.3.
- Proteinuria: Grade 2: urine dipstick proteinuria 2+ and 3+; if urine dipstick proteinuria 4+, check 24-hour urine protein, if  $\geq$  3.5g/day, confirms grade 3 proteinuria. If  $<$ 3.5 g/day, follow grade 2 proteinuria schedule

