## **5.2 Treatment eribulin**

Eribulin will be given as IV infusion or slowly infusion within 15 or 30 minutes in a 100 or 250ml of 0.9% NaCl solution. Eribulin will be given on days 1 and 8 of every 21-days cycle. Eribulin will be given prior to Lenvatinib administration on days 1 and 8. Each cycle will last 21 (+/- 3) days. Laboratory tests will be performed within 3 days prior to days 1 and 8 of all cycles to assess toxicity and confirm that it is safe to proceed with treatment (see Section 6.5) for a complete listing of assessments). The dose of eribulin will be calculated based on the BSA at study entry and should only be recalculated if there is >10% change in body weight from baseline. The actual body weight will be used for these calculations.

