## 5.4 Guidelines for dose delays and dose modifications

This part for the guideline is for all phase Ib and phase II patients..

Dose modification is made according to the greatest degree of toxicity that is graded base on Common Terminology Criteria for Adverse Events v4.03 (CTCAE). The CTCAE v4.03 can be downloaded from the CTEP home page. All appropriate treatment areas should have access to a copy of the CTCAE v4.03.

([http://ctep.cancer.gov/protocolDevelopment/electronic\\_applications/ctc.htm#ctc\\_40](http://ctep.cancer.gov/protocolDevelopment/electronic_applications/ctc.htm#ctc_40)).

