### 5.4.1 Hematological toxicities

Toxicity	Adverse event	Dose Reduction/Delay	
		Eribulin	Lenvatinib
Hematologic toxicity attributed to any or all treatment	ANC <1000/mm  or Platelets 25000-74999/mm  within 3 days prior to scheduled therapy	If Day 1: Hold until recovery to ANC >1000/mm  and Platelets >75000/mm  . Resume at same level after recovery If Day 8: Hold until recovery to ANC >1000/mm  and Platelets > 75000/mm  . Resume at same level after recovery	Hold until recovery to ANC > 500/mm  and platelets more than 25000/ mm  , Resume at same level after recovery.
	Platelets <25000/ mm  or Platelets 25000-50000/ mm  complicated	If Day 1: Hold until recovery to Platelets > 75000/ mm  . Resume at same level after recovery	Hold until recovery of Platelets 25000/mm  . Resume at current

	by bleeding, easy bruising, petechiae, or requiring platelet transfusion	If Day 8: Hold until recovery to Platelets > 75000/ mm  . Resume at same level after recovery	dose level.
	Prolonged neutropenia (ANC<500/ mm  for >7 days)	Hold until recovery to ANC>1000/ mm  . Resume at one dose level below current dose level	Hold until recovery to ANC>500/ mm  Resume at same level dose.
	Febrile neutropenia (ANC <1000/ mm  with temperature of >38.5°C)	Hold until recovery to ANC>1000/ mm  . Resume at one dose level below current dose level	Hold until recovery to ANC>1000/ mm  . Resume at same dose level
	Anemia	No reduction or delay	No reduction of delay

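### The hepatic row of 5.4.2 reduces eribulin without a hold or recovery criterion, so re-dosing during unresolved grade 3/4 liver toxicity rests on investigator judgement

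*Combined protocol and SAP*

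**What the plan says.** Section 5.4.2 has one row for grade 3/4 AST, ALT or total bilirubin.

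- **Eribulin cell:** "If during treatment there is grade 3/4 liver toxicity then dose reduce by 1 dose level". That is the whole instruction.
- **Lenvatinib cell, same row:** "Hold until recovery to Grade 1 or baseline", followed by a restart at 14 mg, then 10 mg, then 8 mg at successive occurrences.

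Below the table, a general rule covers grade 3/4 non-hematological events "not specifically mentioned in the table: the investigator could decrease the dose of the responsible drug after returning to grade 1", at the physician's discretion.

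Four other provisions bear on the same decision.

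- **5.4:** "Dose modification is made according to the greatest degree of toxicity", graded by CTCAE v4.03.
- **5.2:** "Laboratory tests will be performed within 3 days prior to days 1 and 8 of all cycles". The stated purpose is to assess toxicity and confirm that treatment can safely go ahead.
- **5.4.3:** day 8 eribulin may be delayed by at most 1 week, and is omitted if toxicity has not improved enough by then.
- **5.5:** a patient leaves therapy for grade 4 toxicity after 2 dose modifications, after 2 consecutive held cycles, or when the treating physician thinks it necessary.

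**The concern.** One laboratory finding triggers two different kinds of instruction. Lenvatinib stops until the liver tests recover. Eribulin is lowered by a level, and nothing says when the lowered dose may be given. The cell is not marked as needing no action, as several neighbouring rows are, so the plan does treat eribulin as requiring a response to liver toxicity.

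The stake is patient safety. Lenvatinib is on hold during the event, so eribulin is the only study drug the patient could still receive. With no liver criterion for its next dose, two investigators, or the two sites named in 10.6, could act differently on the same AST, ALT or bilirubin result. No effect on the type I error or power of the response-rate test is claimed.

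**Working it through.** No formula applies to the main point. The check is a count of the eribulin column in the two tables, followed by a search for any other rule that supplies the missing criterion.

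**Step 1. Rows that change eribulin.**

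| Row | Section | Hold with recovery level? | One-level reduction? |
|---|---|---|---|
| ANC <1000 or platelets 25000–74999 | 5.4.1 | Yes | No |
| Platelets <25000, or 25000–50000 with bleeding, bruising, petechiae or transfusion | 5.4.1 | Yes | No |
| Prolonged neutropenia | 5.4.1 | Yes | Yes |
| Febrile neutropenia | 5.4.1 | Yes | Yes |
| Hepatic, grade 3/4 | 5.4.2 | **No** | Yes |
| Peripheral neuropathy, grade 3/4 | 5.4.2 | Yes | Yes |
| Nausea/vomiting, grade 3/4 | 5.4.2 | Yes | No |
| Stomatitis, above grade 2 | 5.4.2 | Yes | Yes |

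Rows that leave eribulin unchanged: anemia, hypertension, cardiac dysfunction or hemorrhage, proteinuria, QTc prolongation, hand-foot grade 2, hand-foot grade 3/4. That is 7.

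- Total rows: 8 + 7 = 15.
- Rows changing eribulin that start with a hold: 8 − 1 = 7 of 8. The exception is hepatic.
- Rows that reduce eribulin by one level: 5. Of these, 5 − 1 = 4 hold first, and hepatic again does not.

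The other four reducing rows all put the hold before the reduction. Both neutropenia rows hold to ANC >1000 and then say "Resume at one dose level below current dose level". Neuropathy holds to grade 2 or better and then says "Reduce dose by one dose level". Stomatitis begins "Hold until stomatitis has resolved to" grade 1 or better, then resumes one level lower.

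**Step 2. Does another rule supply a liver criterion for eribulin?**

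- **General rule under the 5.4.2 table.** It places the reduction after return to grade 1, but only for events the table does not name. Liver toxicity is named, so the rule does not reach it.
- **5.2 with Tables 7 and 8.** Liver tests will be available. Table 7 lists AST, ALT and total bilirubin before every cycle. Table 8 marks serum chemistry, which includes them, at both eribulin visits in cycles 1 and 2. No value is given above which eribulin must wait.
- **5.4.3.** It applies to day 8 only and does not say what counts as enough improvement in liver tests. Day 1 has no equivalent.
- **5.5.** It limits repeated grade 4 events and prolonged holds, and allows a physician to stop. It sets no hold after a first grade 3/4 event.
- **3.1, criterion 5.** Liver limits are given (bilirubin 1.5, AST/ALT 2.5, or 5 with liver metastases, times the upper normal limit), but for entry only.

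None of the five gives a hepatic re-dosing limit.

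**Step 3. The dose in question.** Section 5.4.3 lists eribulin at 1.1 and 0.7 mg/m². Starting from 1.1, one level down is 0.7, and 0.7 / 1.1 = 0.636, or 64% of the starting dose.

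**The case against.** The strongest reply is that the cell should not be read alone. Section 5.2 makes a safety check compulsory before every eribulin dose, the liver tests are in hand at that check, and 5.5 lets the physician stop treatment. A careful investigator would probably withhold eribulin at grade 3/4. This stands in part. A reader might infer that the protocol directs or expressly permits eribulin through unresolved grade 3/4 liver toxicity. The documents do not support that, because the pre-dose check stands between the cell and the dose. What the check lacks is a liver value, so the decision is one of judgement.

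Second, the cell can be read as setting only the level of the next dose, in line with the greatest-toxicity principle in 5.4. That reading is natural. It leaves open when that dose may be given, which is the point here.

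Third, a mismatch between rows does not prove an error. The table assigns action by drug: seven rows leave eribulin alone, including grade 3/4 cardiac dysfunction or hemorrhage. Holding one drug and only reducing the other could be deliberate. Nothing in the documents shows that eribulin is the likelier cause of liver injury or that reduction alone is unsafe. This too stands, but no rationale is stated, and no other row that acts on eribulin does so without a hold.

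Fourth, the general rule for unnamed events is permissive and does not itself order a hold, so the comparison with it should not be pressed beyond timing. The grade 1 target is also partly a choice: the neuropathy row accepts grade 2.

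**Conclusion.** The gap is real and narrow. The hepatic row is the only one of eight eribulin-modifying rows, and the only one of five that reduce by a level, with no hold or recovery criterion. No other section supplies one. Whether eribulin at 0.7 mg/m² (64% of 1.1) is given during unresolved grade 3/4 liver toxicity therefore depends on the investigator.

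The row count follows directly from the tables. The 64% assumes that the patient is at 1.1 mg/m² when the event occurs. The safety consequence is less certain, because it depends on how investigators use the 5.2 check. The documents give no hepatic event rate, so no number of affected patients can be stated.

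Two further inferences should be resisted. A reader might think that the combined transaminase and bilirubin elevation in 9.1.3 has no dosing rule. That section concerns reporting, and 5.4.2 does give a rule once values reach grade 3/4. A reader might also fold in the absence of an eribulin level below 0.7 mg/m². That is a separate matter common to all the reduction rules, and it has no bearing on the missing hold.

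This is a cheap improvement for patient safety.

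**What to change.** Replace the eribulin cell of the hepatic row with the plan's own wording from elsewhere: "Hold until recovery to Grade 1 or baseline", then "Resume at one dose level below current dose level". Take only the hold and recovery level from the lenvatinib cell, not its fixed 14/10/8 mg steps. Keep the baseline alternative: patients with liver metastases may enter with AST/ALT up to 5 times the upper normal limit, so a grade 1 target alone could ask for better values than they had at entry. Leave the delay limits in 5.4.3 and 5.5 as they are.

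The change is one table cell in an amendment. It will delay or omit a few eribulin doses. A patient whose liver tests do not recover could reach the 5.5 limit of 2 consecutive held cycles (nominally 2 × 21 = 42 days) and come off treatment.

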#### 5.3.1 Schema for dose adjustments if more than 2 patients have DLT

The first 6 patients will be treated with lenvatinib 18 mg/day D1-D21 and eribulin 1.1 mg/m^2 D1 and D8 (Dose level 11). If no more than 2 ( $\leq 2$ ) patients had dose-limiting toxicity (DLT) in the first cycle (3 weeks), then the lenvatinib (18) and eribulin (1.1) combination will be declared safe. If more than 2 ( $> 2$ ) patients have DLT, the investigators will determine which drug is more pertinent to the DLT(s) and then will follow the customized block chart to shift the dose. If lenvatinib is determined to be related to DLT, the next lower dose would be dose level 21. Otherwise, if eribulin is determined to be the likely cause for DLT, the next dose level will be level 12. The lowest dose acceptable would be either dose level 22 or dose level 31. If still more than 2 patients have DLT in the first 6 patients of dose level 22 or level 31, the combination of lenvatinib and eribulin will be considered too toxic in STS patients.

Table 1: dose levels of lenvatinib and eribulin combination

Dose levels*	Lenvatinib	Eribulin
Dose level 11	18mg/day D1-D21	1.1 mg/m  D1, D8
Dose level 21	14mg/day D1-D21	1.1 mg/m  D1, D8
Dose level 31	10mg/day D1-D21	1.1 mg/m  D1, D8
Dose level 12	18mg/day D1-D21	0.7 mg/m  D1, D8
Dose level 22	14 mg/da D1-D21	0.7 mg/m  D1, D8

[figure not shown]

Figure 2. Schematic dose adjustment directions if more than 2 patients have DLT

The Principal Investigator will be responsible to determine the association as to which drug is more likely to be associated with the DLT and the next dose level to be started in the next step of the phase Ib (run-in) phase.

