## 5.5 Duration of the treatment

- Patients may continue on study therapy until disease progression or until unacceptable toxicity occurs.
- Patients will go off study therapy if any of the following occurs:
  - The patient experiences any grade 4 toxicity after 2 dose modifications, as recommended by the protocol. If treatment is held for 2 consecutive treatment cycles due to toxicity, the patient must go off treatment.
  - The patient withdraws consent from treatment or from the study as a whole.
  - There is disease progression.
  - The treating physician feels it is necessary (e.g. due to patient non-compliance or other safety concerns)

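### For a patient already on 14 mg of lenvatinib or less, the hepatic row of section 5.4.2 states a first restart dose that is not below the current dose

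*Combined protocol and SAP*

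**What the plan says.** The hepatic row of section 5.4.2 covers Grade 3/4 AST, ALT or total bilirubin. Lenvatinib is held until the abnormality is back to Grade 1 or baseline. The restart dose then depends on how many hepatic events the patient has had: "Resume at reduced dose of 14 mg po daily if first occurrence", then "reduce to 10 mg po daily on second occurrence and 8 mg po daily on third occurrence". The eribulin cell of the same row lowers eribulin by one level.

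Other lenvatinib cells in the table work from the dose the patient is taking:

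- Hypertension: "optimal antihypertensive therapy; resume at one dose level below current dose level".
- Proteinuria: "Resume at next dose below current dose".
- QTc: "Resume lenvatinib at one dose level below the current dose when QTc prolongation resolves to Grade 0 or 1".

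Section 5.4 states the scope of these tables: "This part for the guideline is for all phase Ib and phase II patients". Section 5.3.1 allows phase Ib to move lenvatinib to 14 mg (levels 21 and 22) or 10 mg (level 31): "The lowest dose acceptable would be either dose level 22 or dose level 31". Under sections 5.3 and 5.3.3, the level found safe becomes the starting dose for later patients. Section 5.4.3 lists the lenvatinib levels as 18, 14, 10 and 8 mg/day and the eribulin levels as 1.1 and 0.7 mg/m². Section 5.5 ends study therapy in several situations, one of which is: "The patient experiences any grade 4 toxicity after 2 dose modifications, as recommended by the protocol".

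**The concern.** The hepatic row gives absolute doses where the hypertension, proteinuria and QTc rows give relative ones. An absolute dose of 14 mg is a reduction only from 18 mg, and the protocol foresees patients below 18 mg at a first hepatic event by two routes:

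- **Lower starting dose.** Phase Ib may select level 21, 22 or 31. Clinically significant related Grade 3/4 non-hematologic toxicity is itself a DLT under section 5.3.2. Liver toxicity attributed to lenvatinib could therefore help set the start at 14 mg, the same dose that the hepatic row then calls reduced.
- **Earlier cut for another toxicity.** The hypertension, proteinuria and QTc rows each take lenvatinib down a level. The cardiac/hemorrhage and hand-foot rows, and the note on Grade 2 events, also permit a lower dose.

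At stake is what happens after serious liver toxicity. A site that follows the number restarts a 14 mg patient at the dose that preceded the event. A site that follows the word has to work out the dose itself. Two institutions enrol competitively (section 10.6), so the two could handle the same case differently. The documents cannot show whether they would.

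**Working it through.** The plan has no figure to reproduce here. The check compares the dose stated in the hepatic row with one step down from the current dose.

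**Inputs.** Ladder 18, 14, 10, 8 mg/day (5.4.3). Row doses 14, 10, 8 mg at hepatic events 1, 2, 3 (5.4.2). Possible starting doses 18 mg (levels 11, 12), 14 mg (levels 21, 22) and 10 mg (level 31) (5.3.1).

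**Step 1: first hepatic event, by current dose.** Change = row dose minus current dose.

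| Current dose | Row states | Change | One step down |
|---|---|---|---|
| 18 mg | 14 mg | 14 − 18 = −4 | 14 mg |
| 14 mg | 14 mg | 14 − 14 = 0 | 10 mg |
| 10 mg | 14 mg | 14 − 10 = +4 | 8 mg |
| 8 mg | 14 mg | 14 − 8 = +6 | none listed |

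The row matches the ladder only at 18 mg. At 14 mg it gives no reduction. At 10 and 8 mg the number cannot be squared with the word reduced.

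**Step 2: hepatic events only, row followed as written.**

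- Start 18 mg: row 18, 14, 10, 8; ladder 18, 14, 10, 8. They agree.
- Start 14 mg: row 14, 14, 10, 8; ladder 14, 10, 8. Each lenvatinib reduction comes one event late.
- Start 10 mg: row 10, 14, 10, 8; ladder 10, 8. The row's number first falls below the starting dose at the third event.

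**Step 3: cases that section 5.5 removes.** I count only lenvatinib reductions after the starting dose, one level each. This is an assumption, because 5.5 does not say which modifications count. If eribulin modifications count too, more Grade 4 cases leave therapy.

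| Start | Current dose | Earlier reductions | Hepatic events still governed by the row |
|---|---|---|---|
| 18 mg | 14 mg | 1 | Grade 3 and 4 |
| 18 mg | 10 mg | 2 | Grade 3 |
| 18 mg | 8 mg | 3 | Grade 3 |
| 14 mg | 14 mg | 0 | Grade 3 and 4 |
| 14 mg | 10 mg | 1 | Grade 3 and 4 |
| 14 mg | 8 mg | 2 | Grade 3 |
| 10 mg | 10 mg | 0 | Grade 3 and 4 |
| 10 mg | 8 mg | 1 | Grade 3 and 4 |

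The Grade 4 rule narrows the problem without closing it.

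**Step 4: the eribulin cut in the same row.** From 1.1 mg/m² the patient goes to 0.7 mg/m², so the combination is reduced even where lenvatinib is not. From 0.7 mg/m² no lower level is listed. At level 22 (lenvatinib 14 mg, eribulin 0.7 mg/m²), a first hepatic event therefore leads to no stated reduction of either drug.

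**Step 5: text that might repair the cell.** The note giving the physician discretion is confined to toxicities absent from the table, and hepatic toxicity is in it. The hepatic row does not refer to section 5.4.3, and no text limits the restart to the lower of 14 mg and the next level down.

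**The case against.** The strongest reply is that no competent investigator would be misled. The cell says the dose is to be reduced and the ladder is printed in 5.4.3, so the next level down is easily inferred. This stands in part, and it rules out two stronger readings that a reader might reach:

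- *The protocol orders an increase from 10 or 8 mg to 14 mg.* The wording shows that a reduction is meant. The +4 and +6 mg in the first table measure the contradiction in the cell and are not prescribed escalations.
- *Such a patient has no lower dose available.* The ladder gives 10 and 8 mg below 14, and 8 mg below 10. Only at 8 mg is nothing left.

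Other limits also stand. The scheme is built around 18 mg, which the synopsis calls the expected dose and 5.4.3 labels level 0, and the documents do not show that phase Ib went lower. Lenvatinib is restarted only after recovery, and eribulin is cut in the same row where a lower level exists. Besides its Grade 4 rule, section 5.5 removes a patient whose treatment is held for 2 consecutive cycles because of toxicity, and it lets the treating physician stop for safety. The cardiac/hemorrhage and hand-foot rows leave the restart dose partly to the clinician, so clinician choice is not in itself a defect in this protocol.

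None of this makes the stated number right. The rows that leave the dose open do not also print a number that fails to reduce it. A lower starting dose would not break the relative rows: stepping down from 14 mg still gives 10 mg on the ladder. Only the fixed hepatic doses fail.

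**Conclusion.** The point holds as a minor patient-safety correction. The first-occurrence lenvatinib dose in the hepatic row is right from 18 mg, gives no reduction from 14 mg (14 where the ladder gives 10), and contradicts its own wording from 10 or 8 mg.

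This rests on two readings: that occurrence counts hepatic events, which is the natural sense in a row about liver toxicity, and that one step down the ladder is the intended reduction, as in the hypertension, proteinuria and QTc rows. If phase Ib confirms 18 mg (level 11 or 12), only patients already cut for another toxicity are exposed. The documents give no event rates, so the number affected cannot be estimated.

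A reader might also infer that the efficacy analysis is affected. Nothing in the documents supports that: the sample size, error rates and primary endpoint definition do not depend on this cell.

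**What to change.** In the lenvatinib cell of the hepatic row, keep the existing hold condition and replace the three fixed doses with text such as: *Restart one level below the dose being taken, on the section 5.4.3 ladder (18, 14, 10, 8 mg/day). If the patient is already on 8 mg/day, discontinue lenvatinib.*

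The clinical team should confirm the action at 8 mg, since the protocol does not currently state one and stopping is a proposal. The sequence 14, 10, 8 mg is unchanged for a patient who starts at 18 mg and has only hepatic events.

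The cost is one table cell in a wording amendment, with no effect on sample size or analysis.
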